### **4.3.3. Anterior Segment Examination**

The anterior segment examination data is collected on the slit lamp examination eCRF page. The anterior segment examination is performed throughout the study for the study eye and at screening and end of study only for the fellow eye. The following endpoints will be investigated for the study eye and fellow eye (screening and end of study only):

- Abnormal reaction to light
- Active inflammation present in cornea
- Abnormal anterior chamber
- Any opacity in lens. Note if response to lens question is missing but anterior chamber response is normal then response will be defined as no opacity in the lens.
- Aqueous reaction - flare (0, trace, 1+, 2-3+, 4+). Note if response to aqueous reaction flare question is missing but anterior chamber response is normal then response will be defined as 0.
- Aqueous reaction - cells (0, trace, 1+, 2+, 3+, 4+). Note if response to aqueous reaction cells question is missing but anterior chamber response is normal then response will be defined as 0.

### **4.3.4. Posterior Segment Examination**

The posterior segment examination data is collected on the dilated binocular indirect ophthalmoscopy eCRF page. The posterior segment examination is performed throughout the study for the study eye and at screening and end of study only for the fellow eye. The following endpoints will be investigated for the study eye and fellow eye (screening and end of study only):

- Posterior segment abnormalities (none, mild, moderate, severe)
- Presence of posterior vitreous detachment
- Presence of retinal haemorrhage/detachment
- Vitreal haemorrhage density (none, 1+, 2+, 3+, 4+)
- Vitreous cells evaluation (none, 1+, 2+, 3+, 4+)

### **4.3.5. LOCS III Lens**

If an abnormal lens finding is noted during the anterior segment (slit lamp) examination, at any visit, then the finding should be further characterized with LOCS III. All subsequent visits for that subject will include LOCS III. LOCS III is used to grade the severity of age-related cataracts. LOCS III

## Statistical Analysis Plan

---

grading will not be assessed for pseudophakic and aphakic subjects as they do not have opacity.

For the subset of subjects having this additional ophthalmology assessment, the endpoints are:

- [NO] nuclear opalescence (range 0.1 to 6.9)
- [NC] nuclear color (range 0.1 to 6.9)
- [C] cortical cataract (range 0.1 to 5.9)
- [P] posterior subscapular cataract (range 0.1 to 5.9)

For all endpoints a value of 0.1 represents a completely clear or colourless lens. Baseline will be taken as the last available non-missing assessment prior to first study drug administration. For subjects who do not have a baseline measurement for LOCS III but have a baseline anterior segment assessment which confirms no opacity in the lens, then it will be assumed that there were no abnormal lens findings at baseline and a value of 0.1 will be assigned to each of the endpoints. If the baseline anterior segment assessment does not confirm opacity of the lens or is missing then the baseline for the LOCS III endpoints will be taken as missing.

The change from baseline in each of the endpoints will be assessed.

### **4.3.6. Other Safety Endpoints**

Safety will also be assessed through vital signs, laboratory safety data and antigenicity data. Changes from baseline will be calculated taking baseline as the last measurement prior to the first injection.

### **4.4. PHARMACOKINETIC ENDPOINTS**

Plasma APL-2 concentrations will be determined from multiple samples taken during the course of the study - screening, and at each visit from Day 7 to termination (Day 540).

$C_{max}$  should occur at Day 7 ( $C_{Day 7}$ ).

### **4.5. PHARMACODYNAMIC ENDPOINTS**

The pharmacodynamic (PD) endpoints include changes from baseline and percentage changes from baseline for the complement parameters CH50 and C3. Baseline will be taken as the last available non-missing assessment prior to first study drug administration.

## **5. ANALYSIS SETS**

### **5.1. SCREENED POPULATION**

The screened population will include all subjects who signed the informed consent form and are screened for participation in this study. This population will only be used for the purposes of

## Statistical Analysis Plan

---

describing the subject disposition and for listing the data.

### **5.2. RANDOMIZED POPULATION**

The randomised population will include all randomized subjects. This population will only be used for the purposes of describing the subject disposition.

### **5.3. SAFETY POPULATION**

The safety population will include all subjects randomized who receive at least one injection of study medication. The safety population summary groups will be based on the actual treatment received for the whole duration of the study. The grouping rule for subjects who receive study medication from the incorrect injection during the study will be decided on a case by case basis before database lock. This population will be used for all safety analyses.

### **5.4. INTENT TO TREAT (ITT) POPULATION**

The ITT population will include all subjects randomized who receive at least one injection of study medication. Subjects will be included in their randomized treatment group even if they receive the wrong study medication.

### **5.5. MODIFIED INTENT TO TREAT (MITT) POPULATION**

The MITT population will include all subjects randomized who receive at least one injection of study medication and have at least one visit at or after Month 2 where primary efficacy data is collected. Month 2 is the first visit on-treatment where lesion area is measured. Subjects will be included in their randomized treatment group even if they receive the wrong study medication. This population will be used for the primary efficacy analysis and other analyses for efficacy and exploratory endpoints.

If the MITT and the ITT do not differ then only the ITT will be used. If there are minimal differences between these 2 populations then a decision will be made prior to database lock on whether to only use one of these populations for reporting.

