11.1 Populations for analysis

11.1.1 Primary Efficacy Analysis

The primary efficacy analysis will be based on a modified intention-to-treat population (mITT), which is defined as all randomized subjects who receive at least one dose of treatment and have at least one visit at or after month 2. Month 2 is the first visit on treatment at which lesion area is measured.

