#### **8.1. PRIMARY EFFICACY ENDPOINT AND ANALYSIS**

The primary endpoint is the change from baseline in square root area for GA lesion at Month 12 as measured by FAF. Baseline will be taken as the last available non-missing assessment prior to first study drug administration, this should be the screening assessment for the primary endpoint.

The change from baseline in square root area for GA lesion at Month 2, 6 and 12 will be analysed for the MITT population with a MMRM. The model will include the fixed effects of treatment (3 groups: AM, AEOM and Sham), baseline square root area for GA lesion, visit (2, 6 and 12 months), treatment by visit interaction, visit by baseline interaction and treatment by baseline interaction. An unstructured covariance structure will be used to model the within subject error. The Kenward-Rogers approximation will be used to estimate the denominator degrees of freedom. If the treatment by baseline interaction is not significant at the 10% level then this term will be removed from the model. If significant at the 10% level results will be presented both including and excluding this term and the nature of the interaction will be investigated before deciding on an approach for presenting results that include the treatment by baseline interaction.

All available data will be included in the analysis. The analysis model table will be presented. The treatment comparisons (AM vs Sham, AEOM vs Sham and AM vs AEOM) at Months 2, 6 and 12 will also be presented with the estimate, standard error and 95% CI. If the treatment effect is significant at the 10% level then the treatment means will be compared using the least significant difference (LSD) method and the p-value presented. In addition, the estimated mean (i.e. Least-Squares mean) change from baseline in square root area for GA lesion with  $\pm$  SE of mean change, will be plotted over time by treatment group.

The model assumptions will be checked by evaluating the model residuals. A Shapiro-Wilks test will

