### **8.2. SECONDARY AND EXPLORATORY EFFICACY ENDPOINTS AND ANALYSIS**

#### **8.2.1. Best-Corrected Visual Acuity (BCVA)**

The change from baseline in BCVA score over time to Month 12 will be analysed in the same way as the primary endpoint for the MITT population. The model will include the fixed effects of treatment (3 groups: AM, AEOM and Sham), baseline BCVA score, visit (Day 7, Months 2, 4, 6, 8, 10 and 12), treatment by visit interaction, visit by baseline interaction and treatment by baseline interaction. An unstructured covariance structure will be used to model the within subject error. The Kenward-Rogers approximation will be used to estimate the denominator degrees of freedom. If the treatment by baseline interaction is not significant at the 10% level then this term will be removed from the model. If significant at the 10% level results will be presented both including and excluding this term and the nature of the interaction will be investigated before deciding on an approach for presenting results including the treatment by baseline interaction.

The analysis model table will be presented. The treatment comparisons (AM vs Sham, AEOM vs Sham and AM vs AEOM) at Months 6 and 12 will also be presented with the estimate, standard error and 95% CI. If the treatment effect is significant at the 10% level then the treatment means will be compared using the least significant difference (LSD) method and the p-value presented.

The change from baseline in BCVA score will be summarized by treatment group and visit for the MITT population using the observed data. Summaries will present the descriptive statistics for baseline, absolute values and change from baseline data.

The estimated mean change from baseline in BCVA score  $\pm$  SE of mean change, will be plotted over time by treatment group. The plot will be repeated for the observed mean change from baseline in BCVA score  $\pm$  SE of mean change.

The categorical changes (improvements of  $\geq 5$  to  $<10$ ,  $\geq 10$  to  $<15$  and  $\geq 15$ , minimal/no change, worsening of  $\geq 5$  to  $<10$ ,  $\geq 10$  to  $<15$  and  $\geq 15$ , and missing changes) will be summarized by treatment group and visit for the MITT population.

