### **8.2.2. Macular Neovascularization (MNV)**

The incidence and exposure adjusted incidence of macular neovascularization (MNV) TEAEs in the study eye will be summarized for the MITT population.

Exposure adjusted incidence (or incidence rate per 100-patient-years) = number of subjects experiencing MNV / total subject time at risk (in years) × 100

Total subject time at risk is the time from first study drug administration date to first MNV event date +1 for subjects who experience an event, or time from first study drug administration date to last visit date +1 for subjects who do not experience a MNV event. Total subject time will be presented in years with a year = 360 days for the calculation.

The incidence for the MITT population will be compared between the active treatment groups (APL-2 Monthly or APL-2 EOM) and sham group using a Fisher's exact chi-squared test. The analysis will be repeated by the subgroup fellow eye CNV at baseline.

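### MITT membership depends on an autofluorescence assessment at or after Month 2, yet the SAP also uses this set for MNV and visual acuity, so dosed subjects who withdraw early leave analyses that need no such image.

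*SAP*

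**What the plan says.** - **Entry to MITT.** SAP 5.5 requires randomization, at least one injection, and that the subject "have at least one visit at or after Month 2 where primary efficacy data is collected". SAP 8.1 shows which data are meant: "The primary endpoint is the change from baseline in square root area for GA lesion at Month 12 as measured by FAF".
- **Scope of MITT.** SAP 5.5 continues: "This population will be used for the primary efficacy analysis and other analyses for efficacy and exploratory endpoints".
- **Protocol.** Section 11.1.1 introduces the set for one purpose: "The primary efficacy analysis will be based on a modified intention-to-treat population (mITT"). It covers randomized subjects "who receive at least one dose of treatment and have at least one visit at or after month 2". The protocol assigns no population to the secondary endpoints.
- **Acuity.** SAP 8.2.1 states that change in BCVA "will be analysed in the same way as the primary endpoint for the MITT population", and the model's visit factor is "visit (Day 7, Months 2, 4, 6, 8, 10 and 12"). SAP 8.2.3 (LL-BCVA) and 8.2.4 (LL-VA deficit) follow the same approach in the same set.
- **MNV.** SAP 8.2.2 states: "The incidence and exposure adjusted incidence of macular neovascularization (MNV) TEAEs in the study eye will be summarized for the MITT population". The Fisher test of each APL-2 group against sham uses the same set, and time at risk runs from the first administration of study drug. Under SAP 4.2.2, cases are identified by clinical review of ocular adverse events.
- **Safety.** SAP 5.3 and 11 place safety evaluation in the safety population, which is every randomized subject with at least one injection.
- **Fallback.** SAP 5.5 uses ITT alone if the two sets coincide. If they differ slightly, it leaves the choice of set to a decision before database lock and gives no threshold.

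**The concern.** A lesion-area measurement at or after Month 2 is a sensible entry condition for an analysis of lesion growth. It has no function for MNV, which is counted from adverse events, or for acuity, which is tested at every visit and modelled from Day 7. Applied to those endpoints, it selects subjects on something that happens after randomization and may be related to arm and outcome. Sham subjects have no needle entry (Protocol 7.3.3), and Protocol 4.3 lists endophthalmitis, traumatic cataract, retinal detachment and hemorrhage as risks of a real injection. Early withdrawal could therefore differ between arms.

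MNV is where this matters most. Protocol 4.3 already reports more new exudation in eyes given APL-2, particularly with monthly dosing. The only formal test of MNV and its only exposure-adjusted rate are nevertheless confined to subjects known to have reached a later FAF assessment.

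**Working it through.** **1. Does each endpoint need the entry condition?**

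| Endpoint (SAP section) | Source of data | First possible contribution | FAF needed? |
|---|---|---|---|
| Lesion area (8.1), foveal distance (8.2.5) | FAF | Month 2 | Yes |
| BCVA, LL-BCVA, LL-VA deficit (8.2.1, 8.2.3, 8.2.4) | Acuity test | Day 7 | No |
| MNV (8.2.2) | Ocular adverse events | First dose | No |

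**2. Who is removed?** Stopping treatment does not remove a subject, because those who stop can keep attending (Protocol 8.1, 10.5.1) and their assessments are analysed (SAP 6.1). Removal needs full withdrawal before a qualifying FAF. The termination visit includes FAF of both eyes (Protocol 8.3.6), and the Month 2 analysis window opens on study day 47 (SAP 6.3, Table 2). A subject who leaves from day 47 on and completes that visit can qualify. The effective cut-off therefore lies between about day 47 and the nominal Month 2 visit at day 60.

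**3. How many?** The documents give only total loss, 15-20% (Protocol 11.3.4). The plan's own inflation reproduces: 201 / 0.835 = 240.7, against 240 stated. Assumption: loss is spread evenly over 360 days. Number removed = N × loss × cut-off / 360.

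| Loss | Cut-off | Of 240 | Per 80 |
|---|---|---|---|
| 15% | day 47 | 240 × 0.15 × 47/360 = 4.7 | 1.6 |
| 20% | day 47 | 240 × 0.20 × 47/360 = 6.3 | 2.1 |
| 15% | day 60 | 240 × 0.15 × 60/360 = 6.0 | 2.0 |
| 20% | day 60 | 240 × 0.20 × 60/360 = 8.0 | 2.7 |

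**4. What can that do to the MNV comparison?** The counts below are assumed for illustration. Sham is 1/80, and the test is two-sided Fisher at the plan's 0.1 level.

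| Case | All dosed | MITT |
|---|---|---|
| 2 of 7 APL-2 cases withdraw before a qualifying FAF | 7/80 (8.75%), p = 0.064 | 5/78 (6.4%), p = 0.114 |
| 1 event-free APL-2 subject withdraws early | 6/80 (7.5%), p = 0.117 | 6/79 (7.6%), p = 0.064 |

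The first row moves the result towards APL-2 and the second moves it away. Two cautions apply. The first row assumes that essentially all of the roughly two early losses in that arm are MNV cases, which is extreme. In the second row the rate barely moves. With equal groups the two-sided p-value is twice the upper tail (2 × 0.058 = 0.117); with 79 against 80 the mirror-image table no longer counts, while the upper tail itself only changes from 0.058 to 0.056. That jump shows how sensitive the exact test is to set membership, not that the evidence has changed.

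**5. What can it do to acuity?** Days 17-46 map to Month 1 (SAP Table 2), which is not a visit in the acuity model. Moving to ITT would therefore add to the model only values in the Day 7 window (days 2-16). One eye losing 40 letters in an arm of 80 shifts the Day 7 mean by 40/80 = 0.5 letter. Contrasts are presented at Months 6 and 12, where such a subject contributes only indirectly through the within-subject covariance. The categorical tables do change: SAP 6.1 makes the population size the default denominator, and 8.2.1 includes a category for missing changes.

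**The case against.** **MNV events are not hidden.** Study-eye treatment-emergent events are tabulated by arm in the safety population (SAP 11.1). This stands, and it limits the problem to the dedicated incidence, exposure-adjusted rate and test.

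**The protocol is not contradicted.** It lists MNV as a secondary efficacy endpoint and prescribes no population for secondary endpoints, so using an efficacy set breaks no protocol rule. This also stands. The point is that the entry condition does not fit the endpoint.

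**SAP 5.5 already allows a fallback to ITT.** This helps only in part. It is automatic only when the sets are identical; otherwise the choice is made later without a criterion, while sponsor and CRO personnel are unmasked (SAP 3.4). No ITT repeat is planned for acuity or MNV.

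**Stronger readings that a reader might infer.**
- That the MNV and acuity comparisons are biased in favor of APL-2. The documents do not support a fixed direction. A subject lost to endophthalmitis or hemorrhage without MNV leaves only the denominator, which raises the APL-2 MNV rate.
- That any early injection complication removes a subject. It does not, unless the subject withdraws fully before a qualifying FAF.
- That the 0.5-letter shift carries to Month 12. It applies to the Day 7 mean.
- That subjects with clouded media are certainly excluded. This would need no usable FAF at any visit from Month 2 on, and a reading of SAP 5.5 as requiring a gradable image. The wording leaves that open.

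**Conclusion.** The point holds as a mismatch between an analysis set and some of the endpoints assigned to it. The formal MNV comparison carries a selection after randomization that serves no purpose there, and it sits awkwardly with the SAP's own rule for safety evaluation. About 5 to 8 of 240 subjects, or 1.6 to 2.7 per 80, would be affected if the planned 15-20% loss is even over 360 days and the cut-off lies between day 47 and day 60; the true early-loss rate is not in the documents. With few MNV events, one or two subjects can move the Fisher result across 0.1 in either direction. For acuity the effect is small: Day 7 results and categorical denominators change, while the Month 6 and Month 12 MMRM contrasts would move little. The primary analysis is not affected.

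**What to change.** - **SAP 8.2.2:** run the MNV incidence, exposure-adjusted rate and Fisher test on all dosed subjects (the safety population), with MITT as a supportive repeat.
- **SAP 8.2.1, 8.2.3 and 8.2.4:** replace MITT with the ITT population of SAP 5.4. The MMRM can already use a subject whose only post-baseline value is at Day 7.
- **SAP 5.5:** keep MITT for the FAF-based endpoints (8.1, 8.2.5) and narrow the sentence on its scope to match.

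Both replacement sets are already defined and the data are already collected. The cost is SAP wording and a change of population in the affected tables, plus one supportive MNV table. No subjects are lost from any analysis.

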### **5.6. PER PROTOCOL (PP) POPULATION**

The PP population will include all subjects in the MITT population who have not violated any inclusion or exclusion criteria and/or deviated from the protocol, in a way that could influence their efficacy assessment. Subjects will be excluded if they:

- Received less than 75% of their expected injections prior to Month 12. For subjects receiving monthly injections this will be less than 9 injections and for subjects receiving injections EOM this will be less than 4 injections.

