8.3.2 Initial Treatment – Day 0 – Within 14 Days of screening

Visit 2 – All groups

Unless specified, all ophthalmic procedures (including imaging) are to be performed on the **study eye only**.

1. Verify that all inclusion/exclusion criteria are met, including the determination of eligibility by the CRC.
2. Obtain information on any changes in medical health and/or the use of concomitant medications.
3. Collect vital signs pre- and post-dose. Vital signs will be measured within approximately 1 hour prior to dosing for the pre-dose time point. Post-dose vital signs readings will be performed within 30 minutes after dosing.
4. Perform BCVA.
5. Perform LL-BCVA.
6. Perform a complete ophthalmic exam including slit-lamp exam of the cornea, iris, anterior chamber, lens (LOCS III if any opacity on the lens noted) and aqueous reaction (cells and flare), dilated fundus exam of the vitreous and retina and IOP measurement.
7. Use Interactive Web Response (IWR) for subject randomization
8. Perform the IVT injection of APL-2 (or Sham injection) as described in the MOP.
9. Monitor the study eye within 15 minutes post injection as outlined in [Section 9.8](#) and in the MOP.
10. Monitor for adverse events.

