8.3.4 Injection Visits – Monthly or EOM until month 12 -

Monthly Groups: Days 30, 60, 90, 120, 150, 180, 210, 240, 270, 300, 330 and 360 - Visits 4, 5, 6, 7, 8, 9, 10, 11, 12, 13, 14 and 15, respectively.

EOM Groups: Days 60, 120, 180, 240, 300 and 360 – Visits 4, 5, 6, 7, 8 and 9 respectively.

Unless specified, all ophthalmic procedures (including imaging) are to be performed on the **study eye only**. The following procedures will be performed at all injection visits:

1. Obtain information on any changes in medical health and/or the use of concomitant medications.
2. Collect vital signs pre- and post-dose. Vital signs will be measured within approximately 1 hour prior to dosing for the pre-dose time point. Post-dose vital signs readings will be performed within 30 minutes after dosing.
3. Collect blood for PK analysis.
4. Perform urine pregnancy test before APL-2 injection. **-WOCBP only-**
5. Perform BCVA. **-Both eyes on Day 360 only-**
6. Perform LL-BCVA. **-Both eyes on Day 360 only-**
7. Perform a complete ophthalmic exam including slit-lamp exam of the cornea, iris, anterior chamber, lens (LOCS III if any opacity on the lens noted) and aqueous reaction (cells and flare), dilated fundus exam of the vitreous and retina and IOP measurement.
8. Perform the IVT injection of APL-2 (or Sham injection) as described in the MOP.
9. Monitor the study eye within 15 minutes post-injection as outlined in [Section 9.8](#) and in the MOP.
10. Monitor for adverse events.

The following procedures will be performed only at specific visits, as noted:

1. Collect blood and urine for laboratory analysis and forward the samples to the central laboratory. - **Only on Days 60, 180 and 360 for all groups -**
2. Collect blood for genetic marker analysis (if applicable, see [Section 9.3](#)) and forward the samples to the central laboratory. - **Only on Days 60 for all groups -**
3. Perform SD-OCT imaging and forward the images to the CRC. - **Only on Days 60, 180 and 360 for all groups -**
4. Perform FAF imaging **of both eyes** and forward the images to the CRC. - **Only on Days 60, 180 and 360 for all groups -**
5. Perform IR imaging (if applicable) **of both eyes** and forward the images to the CRC. - **Only on Days 60, 180 and 360 for all groups -**

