### **8.1.1. Sensitivity Analyses of the Primary Endpoint**

The robustness of the primary analysis will be evaluated by repeating the primary analysis with the per-protocol population.

In addition, the following sensitivity analyses will be conducted using the MITT population:

- A MMRM analysis including only data which is within a specific time period of the last injection. Month 6 data will be included if a subject was dosed on or after Month 4, and Month 12 will be included if a subject was dosed on or after Month 8. All Month 2 data will be included, as the criteria to be included in the MITT population requires a subject to have had at least one dose of study medication. The primary analysis will be repeated using this subset of data.
- An analysis using an LOCF method for handling missing data as specified in Section 6.2.1. All available Month 12 data will be included and missing data will be replaced using LOCF method. An analysis of Covariance (ANCOVA) model will be fitted for the Month 12 change from baseline in square root area for GA lesion, that includes baseline as a covariate and treatment (3 groups: AM, AEOM and Sham).
- Completer analysis i.e. observed data for those subjects who complete the treatment period (for subjects receiving monthly injections this will be 12 injections and for subjects receiving EOM injections this will be 6 injections) and have their Month 12 assessment. The analysis model will be the same as for the primary analysis.

For each approach, a summary over time will be presented. The analysis model table will be presented. The treatment comparisons (AM vs Sham, AEOM vs Sham and AM vs AEOM) will also be presented with the estimate, standard error and 95% CI. If the treatment effect is significant at

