### **8.1.2. Additional Analyses of the Primary Endpoint**

The completer cases at Month 6 i.e. observed data for those subjects who complete 6 months of treatment (for subjects receiving monthly injections this will be 6 injections and for subjects receiving EOM injections this will be 3 injections) and have their Month 6 assessment; will be analysed using the same model as the primary analysis. This analysis will be repeated for the completer cases at Month 18 i.e. subjects who complete the treatment period (for subjects receiving monthly injections this will be 13 injections and for subjects receiving EOM injections this will be 7 injections) and have their Month 18 assessment.

The untransformed change from baseline in area for GA lesion at Month 2, 6 and 12 will be analysed for the MITT population using the same model as the primary analysis. The estimated mean change from baseline in area for GA lesion with  $\pm$  SE of mean change, will also be plotted over time by treatment group.

Additional summaries and analyses will be performed for the subgroups detailed in Section 6.4. These analyses will be based on the MITT population and will use the same analysis approach as specified in Section 8.1, however the treatment by baseline interaction will only be investigated if it is significant for the primary analysis.

In addition, the observed mean change from baseline in square root area for GA lesion  $\pm$  SE of mean change, will be plotted over time by treatment group and reticular pseudodrusen at baseline (present/absent) on the same plot.

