### **8.1.3. GA Lesion Growth Rate between Timepoints of Interest**

Upon reviewing the 12-month data of the study for the primary analysis, a different growth rate was observed from Month 6 to Month 12 as compared from Baseline to Month 6 for the active group. To assess the growth rate between any two timepoints of interest (Months 6, 12 and 18), the change in GA lesion from Month 6 to Month 12, Month 12 to Month 18, and Month 6 to Month 18 will be summarized. One-way ANOVA will be used to compare the treatment effect on the GA lesion growth between the given timepoints. The pairwise treatment group comparisons will be done based on the least significant different (LSD) t-test to adjust the multiplicity.

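### SAP 5.6: the every-other-month cut-off for the Per Protocol set (fewer than 4 injections) does not match the 75% rule it is meant to express; with 6 expected injections it should be fewer than 5

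*SAP*

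**What the plan says.** SAP 5.6 excludes from the PP set subjects who "Received less than 75% of their expected injections prior to Month 12". The same bullet gives the counts: "For subjects receiving monthly injections this will be less than 9 injections", and "for subjects receiving injections EOM this will be less than 4 injections". It does not say how many injections are expected or whether the first dose is counted.

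The schedule is given elsewhere:

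- All groups are injected at Visit 2, Day 0 (Protocol 8.3.2: "Perform the IVT injection of APL-2 (or Sham injection) as described in the MOP").
- Later EOM injections follow Protocol 8.3.4: "EOM Groups: Days 60, 120, 180, 240, 300 and 360". Monthly injections fall every 30 days from Day 30 to Day 360.
- Protocol 7.3.1 and SAP Table 1 give totals of 13 (monthly) and 7 (EOM), which include both Day 0 and Month 12.
- SAP 8.1.1 defines completers with a Month 12 assessment by 12 monthly injections, and "for subjects receiving EOM injections this will be 6 injections".
- SAP 8.1.2 defines Month 6 completers by 6 monthly injections, and "for subjects receiving EOM injections this will be 3 injections"; for Month 18 completers it uses 13 and 7.

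The PP set serves the first robustness check of the primary endpoint named in SAP 8.1.1.

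**The concern.** One bullet states one rule in two forms, and for the EOM arms the forms disagree. A program written from the percentage and a program written from the count would classify some EOM subjects differently, and the text does not say which form governs. The protocol does not settle it: SAP section 2 says the SAP overrides the protocol on analysis, and SAP section 13, item 1, deliberately replaced the protocol's PP definition.

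The regimens are also held to different standards. Two thirds of the expected doses removes a monthly subject but keeps an EOM subject, although monthly versus EOM APL-2 is one of the planned comparisons. Within the PP analysis, APL-2 EOM subjects who received 4 of 6 doses and still have a Month 12 image could dilute the Month 12 contrasts for that arm.

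**Working it through.** **Expected injections before Month 12 (Day 360), first dose counted**

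- Monthly: Days 0, 30, …, 330 = 12 (that is, 13 − 1).
- EOM: Days 0, 60, 120, 180, 240, 300 = 6 (that is, 7 − 1).

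**Cut-offs.** Exclude if the number received is below 0.75 × the number expected.

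- Monthly: 0.75 × 12 = 9.0, so exclude if fewer than 9. The SAP's figure is reproduced.
- EOM: 0.75 × 6 = 4.5, so exclude if fewer than 5. The SAP's figure of fewer than 4 is not reproduced.

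| EOM injections received of 6 | Share | 75% rule | SAP count |
|---|---|---|---|
| 3 | 50.0% | exclude | exclude |
| 4 | 66.7% | exclude | **keep** |
| 5 | 83.3% | keep | keep |

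For comparison, 8 of 12 monthly doses (66.7%) is excluded under both forms.

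**Other ways of counting the expected injections**

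| Count used | Monthly / EOM expected | 75% | Exclude if fewer than |
|---|---|---|---|
| Day 0 and Month 12 both in | 13 / 7 | 9.75 / 5.25 | 10 / 6 |
| Day 0 in, Month 12 out | 12 / 6 | 9.0 / 4.5 | 9 / 5 |
| Day 0 out, Month 12 in | 12 / 6 | 9.0 / 4.5 | 9 / 5 |
| Both out | 11 / 5 | 8.25 / 3.75 | 9 / 4 |

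Only the last row gives both SAP counts.

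**How many subjects could be affected.** The documents give no missed-dose rate. Assume that every EOM subject receives Day 0 and misses each of the 5 later doses before Month 12 independently with probability p. Exactly 4 of 6 means exactly 2 of those 5 missed: 10 p²(1 − p)³. The planned numbers are 80 on APL-2 EOM and 40 on sham EOM (SAP 3.3), 120 in all.

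| p | Share with 4 of 6 | Of 120 EOM | Of 80 APL-2 EOM | Kept of 80, fewer-than-4 rule | Kept of 80, fewer-than-5 rule |
|---|---|---|---|---|---|
| 5% | 2.1% | 2.6 | 1.7 | 79.9 | 78.2 |
| 10% | 7.3% | 8.7 | 5.8 | 79.3 | 73.5 |
| 15% | 13.8% | 16.6 | 11.1 | 77.9 | 66.8 |

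**Effect on the PP estimate.** Assume further that all these subjects have a Month 12 image and that the planned effect of 0.33 − 0.23 = 0.10 mm (Protocol 11.3.3) scales with the share of doses received. Removing them raises the mean share among those kept from 0.9589 to 0.9653, from 0.9203 to 0.9405, or from 0.8856 to 0.9219. Multiplied by 0.10 mm, the shift is 0.0006, 0.0020 or 0.0036 mm.

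For scale, with SD 0.2 mm and 67 per group, the standard error of a pairwise contrast is 0.2 × √(2/67) = 0.035 mm, so the shift is about 2% to 10% of one standard error.

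**The case against.** The strongest defence is that the authors left out both the first dose and Month 12, giving 11 and 5 expected injections, which reproduces both counts. The convention is not absurd: every MITT subject has had at least one injection, and SAP 7.6 tabulates injections at Months 1 to 12. Nor do the 12 and 6 in SAP 8.1.1 and the 6 and 3 in SAP 8.1.2 settle the matter alone, because they can also be reached by dropping Day 0 and counting the Month 12 or Month 6 injection.

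That much stands, but it does not rescue the text. SAP 5.6 does not state this convention. The 13 and 7 in SAP 8.1.2 and Table 1 count Day 0. Flowchart note G places imaging before dosing, so the natural count up to an image includes Day 0 and omits that visit's injection. The defence also requires Day 0 to be left out of the injections received. A subject with Day 0 plus three later doses then has 3 of 5 (60%) and still fails 75%. So for EOM, fewer than 5 with Day 0 counted is right on either reading. The monthly arm does depend on the reading: 9 doses with Day 0 counted is 9 of 12 (75%, kept) or 8 of 11 (72.7%, excluded). That is one more reason to state the denominator.

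Two further objections concern weight. An explicit integer can be programmed, and PP exclusions were to be reviewed and documented before database lock; this lowers the risk of divergent sets but leaves the contradiction. The independent-miss model is also crude. If the plan's 15–20% loss to follow-up were spread evenly over six dosing intervals, 2.5–3.3% would stop at exactly four doses, about 2 to 3 of 80, and most would have no Month 12 image. The upper figure of 11 of 80 needs 15% misses at every dose. The effect is small, as the working shows.

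**Conclusion.** The concern holds. With 12 and 6 expected injections, the monthly count implements the 75% rule exactly and the EOM count does not: it acts as a 66.7% minimum and keeps subjects with 4 of 6 doses whom the percentage excludes. This follows from the schedule alone and needs no assumption about missed doses.

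The consequence is limited to the PP sensitivity analysis; the primary MITT repeated-measures analysis is unaffected. The subject numbers and the shift of 0.001 to 0.004 mm rest on assumed miss rates of 5% to 15%, independence, full return at Month 12 and an effect proportional to doses received. The case for correction is that the rule contradicts itself and treats the regimens unequally, not that a conclusion is likely to change. It should be corrected.

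**What to change.** In SAP 5.6, change the EOM cut-off to fewer than 5 injections, keep fewer than 9 for monthly, and state the denominators: 12 and 6 injections before Month 12, with the first dose counted among both those expected and those received.

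SAP V3.0 was written after the 12-month results had been seen (SAP 8.1.3: "Upon reviewing the 12-month data of the study for the primary analysis"). The correction should therefore be recorded as made after that review, and the PP results shown under both EOM cut-offs so that the choice cannot appear to be driven by the data.

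The cost is one number, one program line, one extra PP run and a note. There are two drawbacks. The lowest EOM exposure kept becomes 5 of 6 (83.3%), somewhat stricter than the monthly 75%, because no integer out of 6 gives exactly 75%. The APL-2 EOM part of the PP set may also shrink, under the assumptions above to about 78, 73 or 67 of 80 before other exclusions.
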